#### **4.Adverse Event Information**

Not applicable- observational, retrospective study with medical-records analysis.

#### **5.Limitations and Caveats**

1. It was not possible to carry out this analysis for the different types and duration of DM due to the lack of complete data in the analysed medical records coming from the Centre. The disease duration may be connected with higher peak pressure within the feet due to the plantar contact area narrowing (showed previously in dynamic evaluation).
2. The evaluation of the neuropathy in the Diabetic Foot Centre was based on local recommendation and not on e.g. Michigan Neuropathy Screening Instrument (MNSI). However, as a research tool in the mentioned Centre were used: foot inspection, vibration sensation, monofilament testing, and questionnaire for symptoms. This tool was similar to the MNSI.
3. The semi-quantitative analysis of the pressure map (colors), the retrospective nature of the study and the nature of the Center (although the authors involved patients from only one center of a large urban area, the available data seem to be representative of the entire diabetic population).

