**1. Recruitment Details:**

Recruitment period: between October 2009 and December 2010

Type of location: All of the documents were obtained from the Diabetic Foot Centre (DFC) in Wroclaw, Poland, where the patients had consultations, covered a period of fifteen months of work.

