**Pre-assignment Details:**

Patients without previous ulcerations or foot surgery were evaluated- if there were any doubts, the patient's results were not taken into consideration.

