**Arm/Group Information:**

**Arm/Group Title:**

Non-ulcer patients with diabetes mellitus.

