**Arm/Group Description:**

Patients with diabetes mellitus but without active or past foot ulcer or surgical procedure within the feet.

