**Started:**

974 medical records

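### The limitations section calls the data representative of all people with diabetes, which the eligibility rule contradicts and nothing in the documents supports

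*Combined protocol and SAP*

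**What the plan says.** Item 3 of section 5, Limitations and Caveats, names three limitations: the colour-based, semi-quantitative pressure map, then "the retrospective nature of the study and the nature of the Center". A parenthesis concedes that a single centre in a large urban area was used, and sets against this the statement that "the available data seem to be representative of the entire diabetic population".

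Other sections define who was studied:

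- **Source (1. Recruitment Details):** "All of the documents were obtained from the Diabetic Foot Centre (DFC) in Wroclaw, Poland".
- **Group title:** "Non-ulcer patients with diabetes mellitus".
- **Group description:** "Patients with diabetes mellitus but without active or past foot ulcer or surgical procedure within the feet".
- **Pre-assignment Details:** after the restriction to patients without earlier ulceration or foot surgery, "if there were any doubts, the patient's results were not taken into consideration".
- **Started and Completed:** both entries read "974 medical records".
- **Limitations, item 1:** an analysis by diabetes type and duration was not possible "due to the lack of complete data in the analysed medical records coming from the Centre".

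**The concern.** A limitations section tells the reader how far the results may be carried. Here the sentence that raises the limitation also withdraws it, and it names as the target a population wider than the one the study defines.

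This matters because the main results are counts of patients with a condition, and a frequency means something only in relation to the group it describes. A reader who accepts the clause may take the reported frequencies of APD and of peripheral symmetric sensory neuropathy (PSSN) as prevalences among all people with diabetes. That group includes the ulcer and foot-surgery patients whom the study left out.

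The restriction to non-ulcer patients is a legitimate choice and is not in question.

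**Working it through.** The documents give no figure for representativeness, so there is nothing to reproduce. The check sets the clause beside the rest of the text.

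**1. Eligibility against the word *entire*.** The group description removes everyone with an active or past foot ulcer or a foot operation. By rule, the number of such patients analysed is 0 of 974. A sample that excludes a defined subgroup cannot represent a whole that contains it. This step needs no outside figure.

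**2. Record flow.** Started 974 − completed 974 = 0 lost after selection. The number of records screened, excluded for ulcer or surgery, or dropped for doubt is not given. The share of the centre's own patients that was removed is therefore unknown.

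**3. Evidence that could support the clause.** The text contains no sampling frame, weighting, reference or comparison with an external diabetic population. Table 1 under Baseline Characteristics covers sex, age and BMI only, with no population figures beside them.

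**4. Diabetes type and duration.** Item 1 says these could not be analysed, so the sample cannot be compared with any population on them. Item 1 also suggests that duration may be related to peak pressure, which bears directly on the primary outcome.

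**5. The frequencies concerned** (counts from Analysis Population Information):

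- APD: 80 + 894 = 974, and 894/974 = 91.8%.
- PSSN: 907 + 67 = 974, and 67/974 = 6.9%.

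The counts are internally consistent. They describe the sample and do not measure selection.

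**6. Why the bias cannot be sized.** Let *e* be the share of people with diabetes who have an ulcer or foot-surgery history, and *r* the outcome rate among them. Even if the sample rate held for everyone else with diabetes (itself untested), the population rate would be

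(1 − *e*) × sample rate + *e* × *r*.

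Neither *e* nor *r* is in the documents. As an illustration only, with *e* assumed at 5% or 30% and *r* running over its whole range from 0 to 1:

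| Outcome | Sample | *e* = 5% | *e* = 30% |
|---|---|---|---|
| PSSN | 6.9% | 0.95 × 6.88% = 6.5%, up to 6.5% + 5% = 11.5% | 0.70 × 6.88% = 4.8%, up to 4.8% + 30% = 34.8% |
| APD | 91.8% | 0.95 × 91.79% = 87.2%, up to 87.2% + 5% = 92.2% | 0.70 × 91.79% = 64.3%, up to 64.3% + 30% = 94.3% |

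Each range contains the sample rate, so even the direction is open. The conclusion does not rest on these assumed values.

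**The case against.** The best defence is that the parenthesis is about geography. It contrasts representativeness with having one centre in one urban area, not with the eligibility rule, and a reader of the whole document already knows from the group title and description that the patients are non-ulcer patients. The clause is hedged by *seem*, it sits in a section of caveats, and the single centre, the exclusion and the missing data on type and duration are all disclosed. No table or test uses the clause, and the documents print counts, not population prevalences.

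Much of this is fair. Nothing is concealed, no result changes, and no bias has been demonstrated. The rule on doubtful cases most naturally refers to doubt about ulcer or surgery history, so it should not be read as a general purge of records. That 974 is the number left after exclusion is a reasonable inference, not something the documents state.

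The clause is still not rescued. Its wording carries no geographic qualifier. Read as geography alone, it would still need a comparison with other centres or areas, and none is given. A hedge does not supply evidence, and disclosure elsewhere does not correct a sentence that tells the reader the opposite about reach.

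**Conclusion.** The concern holds. The clause attributes to the data a property that the eligibility rule excludes on its literal wording, and that nothing in the documents supports on the narrower geographic reading. The first part follows from the study's own definition of its group and needs no assumption. The second rests on the absence of any supporting material in the available text.

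The direction and size of any bias cannot be determined. Lack of support does not show that the sample is unrepresentative on every characteristic. The within-sample counts and the chi-square tests described in the Statistical Analysis Overview are unaffected. The error is one of scope and should be corrected, because it changes whom the reported frequencies may be said to describe. It does not invalidate the analysis.

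**What to change.** Delete the clause on representativeness from item 3. In its place, state that the frequencies apply to patients with diabetes attending this centre who have never had a foot ulcer and have had no foot surgery, and that wider representativeness has not been shown.

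The cost is a change of wording and a narrower conclusion. No endpoint, count or test changes.

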#### **6.Certain Agreements**

Yes-The principal investigator is an employee of the sponsor.

There is no results disclosure restriction.

